## 8. SAMPLING

Plasma glucose AUC is our primary outcome. No study to date has assessed the effect of hot water immersion on glucose tolerance in individuals with T2DM. Therefore, no data were available to power our primary outcome. For 90% power with an  $\alpha$ -level set at  $P < 0.05$  (two tailed), to detect a 1 SD difference, 13 volunteers are required to compare within group for placebo and active conditions. In order to counterbalance our design, 18 participants will be required to complete the testing. Therefore, we aimed to recruit 20 individuals with T2DM to account for a 10% drop-out rate typically seen in our clinical trials. Resultant effect sizes will be used to power future trials.

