### **13.2 Analysis of Endpoints**

All data will be tested for normality. Normally distributed data will be presented as means  $\pm$  SD. Statistical analyses will be performed on SPSS software version 24.0 (Chicago, IL). For normally distributed data a one-way analysis of variance (ANOVA) will be used to identify differences between conditions for plasma [glucose] (AUC and peak), plasma [insulin], insulin sensitivity, [eHSP70], [IL-6], [IL-10], HRV, NIRS and RMR. Where significance differences are observed, post hoc test will then be performed. Where data is not normally distributed, appropriate non parametric tests will be utilised.

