## 19. DISSEMINATION AND OUTCOME

Results (estimates of effect sizes and confidence intervals) from this study will be utilised to define our primary outcome and to power a larger more complex study. The research is to be disseminated in internationally recognised, peer reviewed journals and at relevant scientific conferences, as well as contributing to [name] PhD thesis. Furthermore, all screening data will be utilised as part of the patient's annual report, and distributed to clinicians and participants upon request.

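### Section 13.2 lets an unspecified normality check choose the primary test for glucose AUC between two loosely named tests, and plans no estimate or interval in either branch

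*Combined protocol and SAP*

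**What the plan says.** Section 13.2 opens with "All data will be tested for normality". It does not say which test is used, at what level, or whether it is applied to raw values, within-person differences or model residuals. Endpoints that pass are compared by one-way ANOVA with post hoc tests, and repeated measures are not mentioned. For the rest, "Where data is not normally distributed, appropriate non parametric tests will be utilised", with no test named. The only summary promised is mean and SD for normally distributed data.

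Section 8 names plasma glucose AUC as the primary outcome, so this rule governs the primary comparison. Section 6.3 describes a within-subject comparison of three conditions. Section 8 also says "Resultant effect sizes will be used to power future trials", and section 19 says "Results (estimates of effect sizes and confidence intervals) from this study will be utilised" to plan a larger study. Section 13.4 states that no statistical analysis plan is needed beyond this text, so no later document is due to fill the gaps.

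**The concern.** In a crossover each person serves as their own control, so the distributional assumption concerns within-person differences or model residuals. How glucose AUC is spread across people cancels out of the comparison. A check on raw values can therefore fail because people differ, even when the paired differences are perfectly well behaved, and the primary test then changes for a reason unrelated to the treatment contrast.

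Three things are at stake. The primary test is settled only after the outcome data are seen, with several choices left to the analyst. Power may be lost, depending on which tests are actually run. And the quantities the trial says it will hand to a larger study, an effect estimate and its interval, are not planned whichever branch is taken.

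**Working it through.** **1. The plan's own figure.** Section 8 states that "13 volunteers are required to compare within group for placebo and active conditions", for a 1 SD difference at 90% power and two-sided 0.05. It does not say which SD. Taking it as the SD of the within-person difference, a paired t test has noncentrality √n on n − 1 degrees of freedom. Power is 88.3% at n = 12 and 91.1% at n = 13, so 13 reproduces. Allowing for dropout, 18/(1 − 0.10) = 20 also reproduces. Power at 18 completers is 97.9%. Two independent groups would need 22 per arm, so the sample size already presumes a paired analysis.

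**2. Inputs that must be assumed.** The documents give no SD, skewness or within-person correlation for glucose AUC. The simulations use n = 18, three conditions and a paired-difference SD of 1, so the error SD is 1/√2 = 0.71 per condition. Both heated conditions are shifted equally from control. Person effects are normal or log-normal. The assumed rule is Shapiro-Wilk at 5% on raw values in each condition; any failure sends the analysis to the Friedman test, otherwise a within-person F test is used.

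**3. How often the rule switches.**
- All data normal: about 13%.
- Log-normal person effects, log-SD 0.3-0.6, between-person SD 0.71-1.5: about 19-55%.
- Checking the two differences from control instead: about 10%.

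Most switches under skewed person effects are therefore needless, since the differences in those data are normal by construction.

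**4. What switching costs with normal within-person errors.** The asymptotic efficiency of Friedman with k = 3 conditions is (3/π) × k/(k + 1) = 0.955 × 0.75 = 0.716, so 18 people act like 18 × 0.716 = 12.9. Simulated power (%) at within-person correlation 0.8, 2,000 trials per cell:

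| Person-effect log-SD | Switch rate | Shift (SD) | Within-person F | Always Friedman | The rule | Between-groups ANOVA |
|---|---|---|---|---|---|---|
| 0 (normal) | 12-13 | 0.5 | 56.6 | 40.8 | 55.2 | 1.3 |
| 0 (normal) | 12-13 | 0.8 | 93.1 | 81.6 | 91.6 | 11.5 |
| 0 (normal) | 12-13 | 1.0 | 99.1 | 94.4 | 98.6 | 33.2 |
| 0.6 | 51-53 | 0.5 | 54.8 | 40.4 | 47.8 | 3.4 |
| 0.6 | 51-53 | 0.8 | 92.8 | 80.6 | 86.4 | 21.7 |
| 0.6 | 51-53 | 1.0 | 99.1 | 94.4 | 97.2 | 44.8 |
| 0.8 | 59-62 | 0.5 | 57.2 | 41.0 | 47.8 | 6.4 |
| 0.8 | 59-62 | 0.8 | 91.6 | 79.2 | 84.5 | 28.7 |
| 0.8 | 59-62 | 1.0 | 98.8 | 94.5 | 96.2 | 50.4 |

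The cost of the rule is the within-person F column minus the rule column. At log-SD 0.6 it is 54.8 − 47.8 = 7.0, 92.8 − 86.4 = 6.4 and 99.1 − 97.2 = 1.9 points. At the more extreme 0.8 it is 9.4, 7.1 and 2.6. At a 0.7 SD shift, over the ranges in step 3, it is about 2-8 points. With no true effect the rule rejects in about 4-5% of trials.

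**5. The ANOVA as literally named.** At 0.7 SD, a between-groups one-way ANOVA has about 4-54% power against about 84% for the within-person F test, because variation between people goes into its error term.

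**6. The reverse case.** At correlation 0.8, log-SD 0.6 and a 0.5 SD shift, Friedman reaches 65% against 62% for the within-person F test when errors are heavy-tailed (t with 3 degrees of freedom), and 84% against 63% when errors are skewed.

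**The case against.** The strongest defence is that the rule does little damage where the trial is powered. At the 1 SD design effect even always using Friedman keeps about 94-95%, above the planned 90%, and the rule itself keeps 96-99%. Type I error does not inflate. An appropriate non-parametric test for a within-subject design would be a paired one, and the paired Wilcoxon test, with efficiency 0.955, loses only about 1-3 points. Section 13.3 keeps outliers in the data, so a rank method has a rationale, and step 6 shows it can win. All of this stands. It limits the size of the problem but does not supply the missing specification. The 1 SD effect was not drawn from data, so performance at smaller effects matters too.

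A reader might infer more than the text supports:
- **That raw values are tested.** This is the natural reading of a check on all data, but the section never says so.
- **That the switch happens often.** The rate rests on assumed skewness and correlation, and is about 13% with normal data.
- **That a sound within-person analysis is exchanged for a weaker one.** The section names only a one-way ANOVA. Read literally, that is the weaker branch, and moving to a paired rank test would gain power.
- **That rank methods cannot give an effect size.** A paired rank analysis can carry a Hodges-Lehmann estimate and interval. The gap is that no estimate is planned in either branch.

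**Conclusion.** The point holds as a specification defect in the primary analysis, and it should be corrected. An unspecified check chooses the test from the outcome data, the parametric branch is not stated to be within-person, the fallback is unnamed, and the estimates that sections 8 and 19 depend on are not planned.

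The harm from switching itself is modest: about 2-8 power points at 0.7 SD and 0-2 points at 1 SD (2.6 in the most skewed case tried). That assumes a raw-value Shapiro-Wilk check, a Friedman fallback and normal within-person errors, and it shrinks or reverses with a Wilcoxon fallback or non-normal errors. The potentially large loss comes from running the ANOVA as between-groups. The documents do not commit to that, but do not exclude it either. A claim of inflated false positives would not be supported.

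**What to change.** In section 13.2:
- Pre-specify one within-person linear model (repeated-measures or mixed) for glucose AUC. Report mean differences between conditions with 95% confidence intervals, whatever a normality test shows.
- Check residuals or within-person differences, not raw values.
- Name one paired sensitivity analysis, for example Wilcoxon with a Hodges-Lehmann estimate and interval, or a permutation test.

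This takes two or three sentences and no new data. The downside is small: with 18 people the interval relies on roughly normal differences, and a rank test can be more powerful when errors are skewed or heavy-tailed. The named sensitivity analysis covers that case.

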### **13.3 Procedure for Dealing with Missing, Unused and Spurious Data**

Outliers will remain within the data. Within the data analysis software missing data will be coded 9999 and the data point will be missed during analysis.

### **13.4 Procedures for Reporting any Deviation(s) from the Original Statistical Analysis Plan**

For this study a statistical analysis plan is not required (excluding the above).

### **13.5 Interim analysis and criteria for early study termination**

Due to the small samples size and time frame, no interim analysis will be performed. Early termination will only occur if the safety of participants is in question.

## **14. ETHICS**

NHS Local Research Ethics Committee (REC) approval will be obtained prior to commencement of the study. The REC, local NHS, research and development department and all site specific forms and patient identification centre forms will be forwarded to the R&D department at Queen Alexandra Hospital Portsmouth, prior to recruitment of participants. Written informed consent will be obtained from all participants. Insurance indemnity will be provided by the University of Portsmouth for this study.

Every effort has been made to keep the risks and discomforts to a minimum, with first aid cover and extensive screening procedures in place but there are some risks associated to taking part. Not all volunteers will experience any or all of the risks stated below, but participants will be made aware of them.

The main burden to participants is a 12 h fasting period before their visit. Participants will be asked to cease all hypoglycaemic agents on the morning of testing and will be instructed to bring them with them on the day. This is in line with a normal fasted OGTT typically used in clinics. Prior to leaving the laboratory, participants will be provided with lunch, they can take their tablets and blood sugars checked prior to leaving.

We will also be asking people with T2DM to be submerged in hot water for condition 2 and 3. This may cause some discomfort which will be assessed with a thermal sensation and comfort scale. We will be measuring the core temperature via rectal thermistor and monitoring it closely at all times. Participants will be reminded that they are free to withdraw at any time point and will also be withdrawn and cooled if  $T_{rec}$  raises above 39°C (as stated in the departments SAP's).

Participants will be asked to insert a rectal thermistor on two out of the four visits (water immersions). This can be uncomfortable upon insertion; however, this is necessary for safety purposes. Participants will be provided with lubrication and instructions.

Other less burdensome tests will be performed such as:

Blood pressure; participants will feel a cuff squeeze their arm and this can be uncomfortable for a few moments. Blood samples taken every 30min via cannulation (using the appropriate hygienic technique and by a trained individual): Intravenous access can cause discomfort associated with insertion of the needle. Infusion of saline (5 mL.30min) will be applied to minimise infection risk (flushing and locking eliminates potential nesting sites for microorganisms) and clotting. To avoid the saline affecting subsequent samples, 2.5 mL of blood will be drawn from the cannula before they are collected.

Other risks that have been accounted for are hypotension and loss of consciousness in the water. If at any point the participants BP is measured at  $\geq 180/100$  the trial will be terminated and the participant withdrawn from the study. If there is loss of consciousness in the water the participant will immediately be harnessed securely out. This can be done quickly as they will already be lying on the sling. Once they are out of the water and placed on a bed, their breathing will be checked and first aid administered. They will also be cooled via cold water spray and a fan. Additionally, their head will never go underwater as their head will be elevated above waterline throughout all submersions.

#### **14.1 Participant Confidentiality**

The study staff will ensure that the participants' anonymity is maintained. The participants will be identified only by initials and a participants ID number on the CRF and any electronic database. All documents will be stored securely and only accessible by study staff and authorised personnel. The study will comply with the Data Protection Act which requires data to be anonymised as soon as it is practical to do so.

#### **14.2 Other Ethical Considerations**

N/A

### **14.3 Declaration of Helsinki**

The study protocol will be carried out in accordance with the Declaration of Helsinki.

### **14.4 ICH Guidelines for Good Clinical Practice**

All research staff exposed to participants will be good clinical practice (GCP) trained and will be monitored by the sponsor to ensure adherence to GCP.

## **15. PATIENT PUBLIC INVOLVEMENT (PPI)**

### **15.1 Study design**

Evidence of patient, carer and public involvement (PCPI):

The chief investigator has a strong track record of PCPI work having been involved in PCPI award winning projects recently from the UK Stroke Forum (October 2016) for another acceptability and feasibility trial. The lay summary and patient facing documentation has been reviewed by our PCPI co-investigator.

### **15.2 Study implementation**

Issues will be managed by the senior members of the research team.

### **15.3 Dissemination**

We endeavour to disseminate findings through local groups, local/national media, research papers and international conferences.

## **16. FINANCING AND INSURANCE**

### **16.1 Research Costs**

The majority of consumables and personnel required for testing have been funded by the University of Portsmouth. All hardware and software is already available.

### **16.2 Service Support Costs**

No service support costs are being sought.

### **16.3 Excess Treatment Costs**

No excess treatment cost are being sought.

### **16.4 Study Sponsorship**

This study is being sponsored by the University of Portsmouth.

## 17. TIMETABLE AND ORGANISATIONAL CHART

February 2018: Funding for consumables has been secured

July 2018: Application for ethical approval

October 2018 - June 2019: Participant recruitment

October 2018 - April 2020: Data collection

April 2020 – June 2020: Data analysis

June 2020: Study completion date

Post-June 2020: Dissemination of results through conference proceedings, journal submissions and practitioner outlets.

## 18. RESOURCES, EQUIPMENT AND PHYSICAL FACILITIES

In addition to the departmental support, and in order to facilitate the completion of the work, the research team will have full access to all of the necessary world-leading extreme environment facilities that are housed within the department estate given that they are pivotal to the success of the project. Specifically, this will enable temperature control within the facilities to ensure reproducibility. Finally, the department will ensure that full technical assistance is provided to enable the set-up of the laboratories and testing rooms.

## 19. DISSEMINATION AND OUTCOME

Results (estimates of effect sizes and confidence intervals) from this study will be utilised to define our primary outcome and to power a larger more complex study. The research is to be disseminated in internationally recognised, peer reviewed journals and at relevant scientific conferences, as well as contributing to [name] PhD thesis. Furthermore, all screening data will be utilised as part of the patient's annual report, and distributed to clinicians and participants upon request.

